## Immediately Reportable Adverse Event (IRAE)

Immediately reportable AEs (IRAEs) are AEs that must be reported to the Sponsor within 24 hours of the study site being informed of the IRAE.

Immediately reportable AEs include

- All Serious Adverse Events (SAEs)
- All AESIs
- AEs that result in a patient's withdrawal from the study (including TEE, fibrinogen inhibitory antibody, suspected allergic reaction)
- Pregnancy

### Serious adverse event (SAE)

An SAE is any untoward medical occurrence or effect that at any dose:

- Results in death,
  - death is an outcome of an AE and not an AE itself. All deaths, regardless of cause or relationship must be reported for patients on study.
- Is life-threatening,
  - life-threatening means that the patient was at immediate risk of death from the event as it occurred. This does not include an event that might have led to death if it were more severe.
- Requires hospitalization or prolongation of existing hospitalization,
  - complications that occur during hospitalizations are AEs. However, if a complication prolongs hospitalization or requires new hospitalization, it is an SAE. In-patient hospitalization means the patient has been formally admitted to a hospital for medical reasons, for any length of time, which may or may not be overnight. It does not include presentation and care within an emergency department. If a patient experiences an AE during dosing and remains in hospital until the AE resolves, this is not considered an SAE unless the investigator considers that the event would have required hospitalization
- Results in persistent or significant disability or incapacity,
- Is a congenital anomaly or birth defect, or
- Is another medically important condition

An important medical event that is not immediately life threatening or will result in death or hospitalization, but which may jeopardize the patient or may require medical intervention to prevent one of the outcomes listed above, should be reported as "serious" as well.

Medical and scientific judgment should be exercised in deciding whether a case is serious.

"Occurring at any dose" does not imply that the patient is receiving study drug at the time of the event.

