### Period:

• Patient Enrolment to the First Administration of Study Drug: Non-treatment emergent AEs will be recorded from the time when the patient is enrolled into the study (date of signature of the informed consent) until first administration of study drug.

- After Administration of Study Drug until respective 49 day visit (Part I and Part II): All TEAEs will be recorded.
- **In-between individual 49 day periods or after last 49 day visit:** Any serious treatment emergent AE considered to be related to the study medication by the investigator will be recorded.

If an AE (serious or not) started after administration of study drug but did not end before the 49 day visit, the investigator should make a reasonable effort to establish the outcome and the end date. If this is not possible, the outcome recorded at the 49 day visit will be assumed to be the final outcome.

If an event stops and later restarts, all the occurrences must be reported. AEs assessed as related to study medication by the investigator and all SAEs must be followed up until resolution.

The investigator should attempt to establish a diagnosis of the event based on signs, symptoms and/or other clinical information. In such cases, the diagnosis should be documented as the AE and/or SAE and not the individual signs/symptoms. Signs/ symptoms should be documented only if a diagnosis cannot be established. If a diagnosis is accompanied by unusual symptoms, the diagnosis itself and the symptoms have to be reported separately.

In addition to the definition as given, the following special types of events should be recorded:

Laboratory values that are outside the normal range and if, in the opinion of the investigator, these values represent a clinically relevant change versus pre-treatment values are also defined as AEs.
 If abnormal laboratory values are signs of an AE (e.g. an infection) that has

If abnormal laboratory values are signs of an AE (e.g. an infection) that has already been recorded, the respective abnormal laboratory value does not constitute a separate AE. Wherever reasonable the reporting investigator will use the clinical term rather than the laboratory term (e.g., anemia versus low hemoglobin value).

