## 14.6.2.1 Responsibilities of Investigator

AE data should be obtained through observation of the patient, from any information volunteered by the patient, or through patient questioning. The general type of question asked could be similar to: "Do you have any health problems?" or "Have you had any health problems since your last clinic visit?"

AEs are to be documented/ recorded accurately and completely on the AE pages of the respective eCRF and in the patient's source data.

All non-treatment emergent AEs will be recorded. During an individual 49 day period all TEAEs are to be recorded. In between individual 49 day periods or after last 49 day visit all serious TEAE considered to be related to the study medication by the investigator will be recorded.

This is true even if the study drug was not administered according to the study protocol.

For conditions leading to unplanned surgical procedures the underlying condition, should be documented as an AE, but not the procedure.

All known information regarding IRAEs must be recorded on the AE log of the eCRF **within 24 hours** of the study center being informed of the IRAE. For IRAEs, all other eCRF pages must be updated or completed as necessary. Electronic CRFs that must be completed for all IRAEs are: patient identification, study drug accountability, demographics, medical history, and concomitant medication. This information must be completed within 24 hours of the study center being informed of the IRAE.

For all IRAEs where important or relevant information is missing, active follow-up should be undertaken.

If for the further evaluation of an AE additional information is required by Biotest's Corporate Drug Safety department, then a representative of the sponsor must be granted access to the medical records. A respective statement has to be integrated in the written informed consent form to ensure adequate assessment of all AEs. Investigators also have the duty to assist in the elucidation of cases and if requested to provide a final written opinion.

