### 14.6.4 Notifying of Adverse Events

### 14.6.4.1 Responsibilities of Investigator

In this study AEs will be reported electronically from the site to the sponsor using the eCRF.

All known information regarding IRAEs (SAEs, AESIs, pregnancy, and AEs leading to withdrawal) must be recorded on the AE log of the eCRF **within 24 hours** of the site learning of the event (see also section 14.6.2.1).

In case the electronic system is not function 24 hours, SAE paper forms will be provided to be used in the case of an IRAE. The paper forms will also need to be faxed or e-mailed to the sponsor within 24 hours of the site learning of the AE.

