5.5 Observation and analysis times

Study periods or stages

The study primarily differentiates between the two parts, part I (PK/PD) and part II (ODP/ODT). Within each part different periods are defined:

Part I:

- Screening period: Day -17 to Day -1
- PK/PD assessment/sampling period:
 - Hospitalization from Day 0 (IV infusion) through Day 2
 - Subsequent PK FU from Day 4 through Day 14
- PK safety FU period ending with the PK safety visit at Day 49 (+/- 4)

Accordingly, the participation time for part I is defined as time from screening visit (ICF date) until PK safety visit and defines the analysis time for part I.

Part II periods differ depending on conduct (with or without hospitalization) but are usually ending with the follow up safety visit at Day 49 (+/- 4). Please see the protocol (e.g. section 3) for more details.

Accordingly, the participation time of patients for part II starts

- ⇒ at screening visit (ICF date) for patients solely enrolled in part II or
- ⇒ at 1st day after part I PK safety visit for patients enrolled into part I/II

and lasts until the date of patients study completion/termination.

For the patient based analysis in part II the analysis time is defined by the participation start time until the safety visit (Day 49 +/- 4) of the patients last treated bleeding event.

For the bleeding event based analysis in part II the analysis time of a bleeding event starts with its Treatment Day 0 and ends with its safety visit. Accordingly, data from in-between

individual 49 day periods or after last Day 49 visit will only be listed and not included in the analysis.

For adverse events reporting related periods are defined:

- Patient Enrolment to the First Administration of Study Drug (NTEAE)
- After first Administration of Study Drug until respective Day 49 visit (part I and part II) (TEAE)
- In-between individual 49 day periods or after last Day 49 visit (only related SAEs will be listed and included in the analysis), all other AEs will be counted and listed.

For concomitant medication please refer to section 9.

Study days and bleeding event number

Primarily, study days are counted since first dose of study medication (i.e. in part I) up until the end of study participation.

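### The protocol requires every death on study to be reported but sets a related-only recording rule outside the 49-day windows, and the SAP does not say how its death count covers that time

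*Protocol*

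**What the plan says.** **Protocol, broad rule.** Under the SAE definition in 14.6.1, "All deaths, regardless of cause or relationship must be reported for patients on study". The same section says that "death is an outcome of an AE and not an AE itself". It also puts SAEs on the list of events to be reported within 24 hours, with no condition on causality or timing. Section 14.6.4.1 gives the route: "All known information regarding IRAEs (SAEs, AESIs, pregnancy, and AEs leading to withdrawal) must be recorded on the AE log of the eCRF".

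**Protocol, narrow rule.** Section 14.6.2 sets recording by period. From administration to the respective Day 49 visit, "All TEAEs will be recorded". Between those periods and after the last Day 49 visit, "Any serious treatment emergent AE considered to be related to the study medication by the investigator will be recorded". Section 14.6.2.1 repeats this among the investigator's duties: "In between individual 49 day periods or after last 49 day visit all serious TEAE considered to be related to the study medication".

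**SAP.** Section 5.5 says that for AEs in the gaps "only related SAEs will be listed and included in the analysis"; the same sentence goes on to say that the remaining AEs are counted and listed. Section 11.1 limits the TEAE analysis to the time from treatment to the safety visit, with related SAEs as the exception. The AE overview on the All Patients Enrolled (APE) set has one row for AEs with a fatal outcome and another for 'Any death'. The safety-set tables include TEAEs leading to death. Section 11.2 lists patients with AEs leading to death.

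**The concern.** The protocol gives sites two rules for the same event. A patient between windows is still on study, so the broad rule applies to any death. The narrow rule covers the fatal event only if the investigator judges it related to BT524.

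All-cause mortality is the safety count that should least depend on a causality judgement, above all in an open-label, uncontrolled study. Here that judgement could decide whether a death in a gap is entered at all. Once entered, it decides whether the death appears in the table of fatal TEAEs or only in a listing.

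**Working it through.** The plan states no figure on this point, so the main check sets the texts side by side.

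**1. Are patients in the gaps on study?** Yes. Protocol 14.6.1 runs the treatment-emergent period from first dose to last study visit. SAP 5.5 runs part II participation to study completion or termination. A part I patient past Day 49 who is waiting for a first part II event is one example.

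**2. Does reporting differ from recording?** Not in a way that removes the conflict. Section 14.6.4.1 has SAEs reported by recording them on the eCRF AE log. Because a death is treated as the outcome of an AE, it reaches the database through a recorded fatal AE.

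**3. Is the narrow rule really restrictive?** The protocol sentence does not contain the word *only*. The contrast with the in-window rule, which takes every TEAE, implies it.

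**4. Which case is exposed?**

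| Fatal AE | 14.6.1 and 14.6.4.1 | 14.6.2 and 14.6.2.1 |
|---|---|---|
| Starts before first dose | Required | Recorded |
| Starts inside a 49-day period, any cause | Required | Recorded; SAEs followed to resolution |
| Starts in a gap, judged related | Required | Recorded |
| Starts in a gap, judged unrelated | Required | Not covered |

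Only the last row conflicts. An example is a fatal event that was not treated with BT524.

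**5. What happens in the SAP if that event is entered?** It is counted and listed under 5.5 and 11.1, and it belongs in the listing of AEs leading to death (Listing 16.9.3, APE I and II). It falls outside the time frames for the table of TEAEs leading to death. For 'Any death', section 11.1 gives neither data source nor period, so whether the row includes the event cannot be determined.

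**6. How much time lies in the gaps?** This is an illustration. Let T = 365 days (part II lasts at least 12 months), w = 49 days with the protocol's ±4, and k = the number of treated events per year. Here k is assumed, with single infusions and non-overlapping windows.

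Share outside windows = 1 − k·w/T

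| k | w = 49 | w = 53 to 45 |
|---|---|---|
| 1 | 1 − 49/365 = 86.6% | 85.5% to 87.7% |
| 2 | 1 − 98/365 = 73.2% | 71.0% to 75.3% |
| 3 | 1 − 147/365 = 59.7% | 56.4% to 63.0% |
| 5 | 1 − 245/365 = 32.9% | 27.4% to 38.4% |

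The window runs from the last administration for an event, so repeated dosing lengthens the covered time and lowers these shares. Participation beyond 12 months with the same number of events raises them.

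**The case against.** The strongest reply is that the protocol imposes the duty more than once. Deaths have their own explicit rule, all SAEs are immediately reportable, and 14.6.4.1 requires them on the AE log. A site that left out an unrelated death would have to disregard all three. This stands, and it is why an undercount is possible rather than certain. It does not remove the conflict: 14.6.2 and 14.6.2.1 are the sections that tell sites what to record and when, they are narrower, and nothing says which rule prevails.

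The second reply is that the SAP does not discard such events. This also stands. A reader might infer from the first half of the SAP 5.5 sentence that unrelated deaths in the gaps vanish, but the second half has them counted and listed, and Listing 16.9.3 carries no window or relatedness limit in its title. What remains is that they are left out of the fatal-TEAE table and that the source and period of 'Any death' are undefined. That row carries no treatment-emergent qualifier and is separate from the fatal-AE row, so it may be meant to be complete; the SAP does not say so.

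The third reply is that the exposed case is narrow. Treating a bleed with BT524 opens a new period in which all TEAEs are recorded, so many bleeds will not stay in a gap. This is fair. An untreated fatal bleed or a death from another cause remains exposed.

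**Conclusion.** The inconsistency is real and no passage resolves it. A fatal AE judged unrelated that starts between 49-day periods or after the last Day 49 visit is required by one set of rules and not covered by the other. If recorded, it stays out of the table of fatal TEAEs, and its place in 'Any death' is undefined.

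Three stronger readings are tempting and are not supported:

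- *That deaths will be missed.* The broad rule, if followed, captures them all.
- *That the SAP promises 'Any death' over the whole study and fails to deliver it.* It states no period, and that omission is the defect.
- *That the share of time in the gaps measures missed deaths.* It is person-time under assumed event rates (about 87%, 73% and 33% of a year with one, two and five single-infusion events). The documents give no expected number of deaths, no fraction judged unrelated and no information on site practice.

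The gaps can be most of a patient's time on study, so the matter should be corrected even though its effect on the count cannot be quantified.

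**What to change.** **Protocol 14.6.2 and 14.6.2.1.** Reconcile with 14.6.1 and 14.6.4.1 by adding that fatal AEs of any cause are recorded from consent to the end of the patient's participation, inside or outside a 49-day period. The same passages also differ for non-fatal unrelated SAEs in the gaps, so the wording should make clear which rule governs those.

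**SAP 5.5 and 11.1.** State that 'Any death' and the fatal-AE tables include all deaths from consent to study completion or termination, regardless of window or relatedness. Name the data source, for example the AE log alone or together with the study-termination page.

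**Cost.** A sentence or two in each document. No visit or assessment is added, and sites take on no duty that 14.6.1 does not already impose. A protocol change acts only on data still to be collected; the SAP clarification can be made in any case.

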## Adverse Event of Special Interest (AESI)

An AE of special interest (serious or non-serious) is one of scientific and medical concern specific to the sponsor's IMP or development program, for which ongoing monitoring and immediate communication by the investigator to the sponsor may be appropriate. Such events may require further investigation in order to characterize and understand them. Reporting / Notifying requirements are detailed in section 14.6.4.

The following AEs have been defined as AESI for this study: Thrombosis or TEE, and suspicion of transmission of infective agents (viral safety).

# Severity of Adverse Event:

Refers to the extent to which an AE affects the patient's daily activities. Severity will be categorized according to the criteria shown in Table 6.

### Table 6: Severity of Adverse Event

Mild:	The AE does not interfere with the patient's routine activities.	
Moderate:	The AE interferes with the patient's daily routine, but usual routine	
	activities can still be carried out.	
Severe:	The AE results in the inability to perform routine activities.	

The term "severity" is used to describe the intensity of an event. This is not the same as "serious". Seriousness, not severity, serves as the guide for defining regulatory reporting obligations. The highest severity grade attained should be reported, for AEs with divergent severities.

## Causality of Adverse Event:

Refers to the relationship of the AE to study drug. Causality will be categorized according to the following criteria:

### Not related:

AEs for which a reasonable explanation for an alternative cause is considered plausible e.g., no study drug taken, plausible clinical alternative like accidental injury, expected progression of underlying or concomitant disease, pharmacologically incompatible temporal relationship, intercurrent illness.

### **Related:**

AEs for which a reasonably possible clinical and/or pharmacological relationship to study drug cannot be excluded e.g., lacking plausible alternatives.

### 14.6.2 Recording Adverse Events

In this study adverse events will be recorded electronically in the eCRF.

### Period:

• Patient Enrolment to the First Administration of Study Drug: Non-treatment emergent AEs will be recorded from the time when the patient is enrolled into the study (date of signature of the informed consent) until first administration of study drug.

- After Administration of Study Drug until respective 49 day visit (Part I and Part II): All TEAEs will be recorded.
- **In-between individual 49 day periods or after last 49 day visit:** Any serious treatment emergent AE considered to be related to the study medication by the investigator will be recorded.

If an AE (serious or not) started after administration of study drug but did not end before the 49 day visit, the investigator should make a reasonable effort to establish the outcome and the end date. If this is not possible, the outcome recorded at the 49 day visit will be assumed to be the final outcome.

If an event stops and later restarts, all the occurrences must be reported. AEs assessed as related to study medication by the investigator and all SAEs must be followed up until resolution.

The investigator should attempt to establish a diagnosis of the event based on signs, symptoms and/or other clinical information. In such cases, the diagnosis should be documented as the AE and/or SAE and not the individual signs/symptoms. Signs/ symptoms should be documented only if a diagnosis cannot be established. If a diagnosis is accompanied by unusual symptoms, the diagnosis itself and the symptoms have to be reported separately.

In addition to the definition as given, the following special types of events should be recorded:

Laboratory values that are outside the normal range and if, in the opinion of the investigator, these values represent a clinically relevant change versus pre-treatment values are also defined as AEs.
 If abnormal laboratory values are signs of an AE (e.g. an infection) that has

If abnormal laboratory values are signs of an AE (e.g. an infection) that has already been recorded, the respective abnormal laboratory value does not constitute a separate AE. Wherever reasonable the reporting investigator will use the clinical term rather than the laboratory term (e.g., anemia versus low hemoglobin value).

## 14.6.2.1 Responsibilities of Investigator

AE data should be obtained through observation of the patient, from any information volunteered by the patient, or through patient questioning. The general type of question asked could be similar to: "Do you have any health problems?" or "Have you had any health problems since your last clinic visit?"

AEs are to be documented/ recorded accurately and completely on the AE pages of the respective eCRF and in the patient's source data.

All non-treatment emergent AEs will be recorded. During an individual 49 day period all TEAEs are to be recorded. In between individual 49 day periods or after last 49 day visit all serious TEAE considered to be related to the study medication by the investigator will be recorded.

This is true even if the study drug was not administered according to the study protocol.

For conditions leading to unplanned surgical procedures the underlying condition, should be documented as an AE, but not the procedure.

All known information regarding IRAEs must be recorded on the AE log of the eCRF **within 24 hours** of the study center being informed of the IRAE. For IRAEs, all other eCRF pages must be updated or completed as necessary. Electronic CRFs that must be completed for all IRAEs are: patient identification, study drug accountability, demographics, medical history, and concomitant medication. This information must be completed within 24 hours of the study center being informed of the IRAE.

For all IRAEs where important or relevant information is missing, active follow-up should be undertaken.

If for the further evaluation of an AE additional information is required by Biotest's Corporate Drug Safety department, then a representative of the sponsor must be granted access to the medical records. A respective statement has to be integrated in the written informed consent form to ensure adequate assessment of all AEs. Investigators also have the duty to assist in the elucidation of cases and if requested to provide a final written opinion.

